### **7.5 Follow-Up Visits**

All study subjects will have follow-up visits at 1, 3 and 6 Months after Baseline to evaluate the joint pain score and to assess adverse events.

The subject should be contacted at least 48 hours prior to their scheduled assessments to be reminded of the required assessment (and applicable wash out period) and to schedule the date and time of contact. At least three documented attempts will be made to contact the subject in order to accomplish maximum subject compliance with the follow-up schedule.

The following tests will be performed at the follow-up visits at 1, 3, and 6 months.

### **7.6 Follow-up Visits ( $\pm$ 7 days)**

- Assess Concomitant Medications
- Assess Non-drug therapies
- Assessment of Adverse Events
- Confirm Rescue Medication Washout
  - If subject did not complete medications washout, reschedule the visit to allow washout to be completed.
- Assess Rescue Medication usage
- Collect and assess subject diary

- Patient Global Assessment (PGA)
- AOFAS index and contralateral joints
- Index & Contralateral Hip, Knee and Ankle Joint Pain on walking (NRS)
- Physical Exam of Index and Contralateral Hip, Knee and Ankle Joints

## 8. ADVERSE EVENTS

### 8.1 Reporting

#### 8.1.1 Adverse Events

All AEs that occur during or after injection will be recorded. Worsening of a condition that existed prior to the study injection should be recorded as an AE. At each assessment during the trial, AEs that have occurred since the previous assessment must be recorded. All subjects will be questioned and evaluated for AEs or complications associated with the procedure. Complications of the injection include, but are not necessarily limited to: pain, swelling, erythema, bleeding and/or infection at the injection site. The Investigator will determine the severity and relationship of each event, as defined above.

AEs observed during the course of this study, regardless of severity or relationship to the injection will be recorded on the CRF. Each reported complication/AE will also include the duration, action taken to address the AE, and the resolution status (e.g. ongoing, resolved). These subjects will continue to be evaluated for safety at all scheduled follow-up points.

#### 8.1.2 Serious Adverse Events/Serious Adverse Device Effects

All SADE/SAEs must be reported to the Sponsor or designee within 24 hours of the investigative site becoming aware of its occurrence. This requirement is irrespective of whether the SADE/SAE is thought to be possibly related to the device or not.

## 9. STATISTICAL CONSIDERATIONS

### 9.1 Sample Size

The primary analysis will be the mean change in index joint pain from baseline to 6 months as measured by the Numerical Rating Scale.

The hypothesis to be tested is:

$$H_0: \mu_{DMON} = 0 \text{ versus } H_A: \mu_{DMON} > 0.$$

In this hypothesis,  $\mu_{DMON}$  is the mean change in pain from baseline at 6 Months in MONOVISC treated patients.

The data will be analyzed via a one sample t-test.

It is assumed that a mean change in pain from baseline of 2 points represents a clinically significant improvement with a standard deviation of 2 - 2.5 points, for 80% power and alpha of 5% then a total of 15 subjects are required. To ensure sufficient subjects are available at the 6 month follow up, it is proposed to enroll and treat at least 25 subjects which should be more than

adequate to demonstrate that treatment of the study population with MONOVISC would reduce joint pain at 6 months.

Single sites should not enroll more than 50% of the total enrollment.

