### **9.2.3 Subject Populations**

The Safety Population will be defined as all subjects who undergo Study Treatment, and the safety analysis will be performed on this population.

The primary analysis on the primary endpoint will be performed on the Intent to Treat (ITT) population, defined as all patients who were treated in the study. All Primary and Secondary endpoints will be analyzed using the ITT population.

A secondary analysis will be conducted on the Per Protocol (PP) population. Since the primary endpoint is at 6 Months, this is all subjects who complete the 6 Month assessment and who do not have a major deviation from the protocol. For all other assessments, this is defined as the subjects who complete those assessments according to the protocol.

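### Run as written, the 6-month one-sample t-test uses only treated subjects with a Month 6 score, although the primary population is all treated; if poor responders leave more often, the pain reduction is overstated

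*Protocol*

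**What the plan says.** Protocol section 9.1 defines the analysis: "The primary analysis will be the mean change in index joint pain from baseline to 6 months as measured by the Numerical Rating Scale". The parameter under test "is the mean change in pain from baseline at 6 Months in MONOVISC treated patients", with positive values meaning less pain. The method follows: "The data will be analyzed via a one sample t-test".

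The same section requires 15 subjects and then adds a margin: "To ensure sufficient subjects are available at the 6 month follow up, it is proposed to enroll and treat at least 25 subjects".

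Section 9.2.3 assigns the primary endpoint to the "Intent to Treat (ITT) population, defined as all patients who were treated in the study". A Month 6 score is not a condition of that set. It is a condition of the Per Protocol set: "this is all subjects who complete the 6 Month assessment and who do not have a major deviation from the protocol".

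The Schedule of Events (section 7.1) has NRS pain collected at Months 1 and 3 as well as Month 6. The protocol does not say how a treated subject without a Month 6 score enters the primary analysis.

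**The concern.** A one-sample t-test of 6-month change needs one 6-month value per subject. If nothing is imputed, its n is the number of subjects with that value. The sample-size text reasons in the same way, because the margin over 15 is justified by availability at 6 months. Run like this, the analysis labelled ITT differs from the Per Protocol analysis only by the exclusion for major deviations.

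This matters if those who leave have done worse than those who stay, and the protocol makes that plausible:

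- Sections 6.6.1 and 7.3.9.1 bar other treatment of the index joint and all analgesics except acetaminophen/paracetamol for the whole study. A subject without relief therefore has a reason to leave.
- Section 13.12 seeks the return of withdrawn subjects for safety evaluations and names no pain score.

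The study has one open-label arm, so there is no control group in which a similar loss could offset the bias. The bias would favour the product.

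**Working it through.** **1. The plan's own figure.** Inputs from section 9.1: mean change 2, SD 2 to 2.5, power 80%, alpha 5%. Exact one-sample t-test power (noncentral t) gives these required numbers:

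| SD | two-sided 5% | one-sided 5% |
|---|---|---|
| 2 | 10 | 8 |
| 2.5 | 15 | 12 |

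The stated 15 is reproduced with SD 2.5 and a two-sided test (power 0.821). With all 25 observed, power is 0.970. The margin is 25 − 15 = 10 subjects, or 10/25 = 40%.

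**2. Bias by arithmetic.** Let f be the share of treated subjects without a Month 6 score. Then

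completer mean − all-treated mean = f × (completer mean − mean of those missing).

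With a completer mean of 2.0 and assumed means for those missing:

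| Missing | f | Mean change of those missing | All-treated mean | Bias |
|---|---|---|---|---|
| 5 of 25 | 0.20 | 0 | 0.8 × 2.0 + 0.2 × 0 = 1.6 | 0.4 |
| 5 of 25 | 0.20 | 1 | 0.8 × 2.0 + 0.2 × 1 = 1.8 | 0.2 |
| 10 of 25 | 0.40 | 0 | 0.6 × 2.0 + 0.4 × 0 = 1.2 | 0.8 |
| 10 of 25 | 0.40 | 1 | 0.6 × 2.0 + 0.4 × 1 = 1.6 | 0.4 |
| either | either | 2 | 2.0 | 0 |

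**3. Simulation, dropout depending on the last observed change.** From the protocol: 25 subjects, a true Month 6 change of 2.0 (the planning value) and SD 2.5 (the upper planning value). Assumed: between-visit correlation 0.6 to 0.7, and log-odds of dropout rising by 0.3 to 0.6 for each point less improvement. There were 4,000 trials per setting.

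| Dropout | Completer mean | Bias |
|---|---|---|
| 10% | 2.1 to 2.2 | 0.1 to 0.2 |
| 20% | 2.2 to 2.4 | 0.2 to 0.4 |
| 30% | 2.4 to 2.6 | 0.4 to 0.6 |
| 40% | 2.5 to 2.8 | 0.5 to 0.8 |

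The repeated-measures estimate was about 2.00 throughout, with a similar standard error. That recovery is built in, because dropout here depends only on observed scores.

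**4. Simulation, dropout depending on the current, unobserved score** (correlation 0.65):

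| Dropout | Slope | Completer mean | Repeated-measures mean | Share of bias remaining |
|---|---|---|---|---|
| 20% | 0.3 | 2.30 | 2.14 | 0.14/0.30 = 47% |
| 20% | 0.6 | 2.51 | 2.25 | 0.25/0.51 = 49% |
| 40% | 0.3 | 2.63 | 2.29 | 0.29/0.63 = 46% |
| 40% | 0.6 | 2.98 | 2.51 | 0.51/0.98 = 52% |

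**5. Effect on the test.** A separate simulation let missingness depend on the 6-month change itself, with assumed odds ratios of about 1.6 to 2.7 per SD, SD 2 to 2.5 and 40,000 runs per setting.

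- True change 2: the two-sided test still rejects at least 94% of the time.
- True change 0: the one-sided 5% test rejects 11% to 20% of the time at 20% missing, and 18% to 38% at 40% missing.
- Missingness unrelated to response: bias is zero and the error rate is nominal.

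**The case against.** The strongest objection is that the t-test and the all-treated population do not contradict each other. A one-sample t-test can be run on all treated subjects once missing scores are imputed. A missing-data rule commonly sits in the SAP, which is not shown. Section 9.2.3 also makes Month 6 completion a Per Protocol condition only, which suggests that ITT is meant to keep non-completers. This stands: a reader might infer that the t-test can only ever be a completer analysis, and the protocol does not say so. The point is limited to the test run as written, without imputation.

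A reader might also infer that the protocol expects to lose 10 of 25. It does not. It states no dropout rate, and the gap between 15 and 25 is a margin. Several provisions should limit loss: rescue medication is allowed (7.3.9.2), at least three contact attempts are required (7.5), visits are rescheduled after incomplete washout (7.6), and subjects with deviations continue to be followed (13.4). None of these recovers a pain score after withdrawal.

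A third inference would be that the estimate is bound to be inflated. It is not: the bias is zero if dropout is unrelated to response, and it reverses if good responders stop attending.

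Finally, the repeated-measures model is not a complete cure. It relies on missing at random and still omits a treated subject with no post-baseline score. Both limits are real and are the reason for the sensitivity analysis.

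The objections do not remove the main reason to act. The protocol names a primary method that makes no use of the Month 1 and Month 3 scores, and a better use of data already collected is available.

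**Conclusion.** The point holds in conditional form. The named primary method, run without imputation, does not deliver the named primary population, and it discards earlier scores that bear on the missing ones. The bias is about 0.1 to 0.8 points on a 2-point planning effect for 10% to 40% dropout driven by the last observed change. It approaches 1 point in the most extreme setting tried (40% dropout, slope 0.6, dropout driven by the unobserved score). All dropout rates, slopes and correlations are assumptions, since the protocol supplies none.

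If the true change is near 2 points, the harm is to the size of the reported reduction and not to the test result. That size matters because section 9.1 takes 2 points as the clinically significant improvement. If the true change is near zero, the error rate of the test also suffers. The change is worth making because it is cheap; the documents do not show that the plan is invalid.

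**What to change.** In sections 9.1 and 9.2:

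1. Make the primary analysis a repeated-measures model of NRS change at Months 1, 3 and 6, with visit as a factor, baseline NRS centred at the mean of all treated subjects, and an unstructured covariance. Report the Month 6 mean change with its 95% CI.
2. Keep the one-sample t-test on observed Month 6 scores as a supportive analysis.
3. Add one sensitivity analysis over all treated subjects, including those with no post-baseline score, that assigns zero change to anyone without a Month 6 score.

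The cost is protocol and SAP wording plus a little more analysis; no new data, visits or subjects are needed. The downside is that the primary estimate then rests on missing at random, removes only about half the bias if dropout follows unobserved pain, and may be slightly less favourable to the product.

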## **9.2 Statistical Methods**

Tabulation of summary statistics, graphical presentations, and statistical analyses will be performed. Where not otherwise specified, the last pre-treatment observation will be used as baseline for calculating post-treatment changes from baseline. The primary presentations and analyses will be based on data pooled across index lesion locations and across study centers. Relevant summaries for individual lesion locations and centers, or combinations of index lesions and centers, may be presented for primary data. All testing and confidence intervals will use a significance level of 5%.

### **9.2.1 Demographic and Baseline Characteristics**

All demographic and baseline characteristics will be tabulated by treatment group. Medical history findings, physical examinations and concomitant medications will be tabulated.

### **9.2.2 Adverse Events**

Subjects with AEs will be summarized with frequencies and percentages by system organ class and preferred term, severity, and relationship to investigational product/procedure. In summaries of AEs by severity and relationship to investigational product/procedure, subjects reporting multiple episodes will be counted once under the worst severity and the strongest relationship, respectively. Serious Adverse Events will also be presented by relationship to investigational product/procedure.

Adverse events occurring prior to the index treatment will not be recorded in this trial.

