#### 4.2 Risks

Any intra-articular injection poses potential risks. However, subjects should incur no additional risks compared to injections of other frequently injected products, such as corticosteroids or diagnostic contrast agents.

Adverse events associated with single intra-articular knee injections of MONOVISC can be found in the MONOVISC Instructions for Use. These events are expected to be similar for ankle injections. In the clinical trial for MONOVISC in knee OA, adverse events that were related to the injection treatment were:

- injection site pain/swelling
- joint stiffness / swelling / effusion
- arthralgia,
- pain in extremity
- synovitis

- contusion
- subcutaneous nodule
- Baker's cyst

Adverse events not related to the index joint for MONOVISC were:

- arthralgia
- headache
- pain in extremity
- upper respiratory tract infection
- back pain

Other risks associated with intra-articular ankle injections, regardless of treatment, include:

- temporary injection site pain, swelling or tenderness
- temporary stiffness of the ankle
- malfunction of the syringe and/or needle

In rare instances, side effects could include:

- an allergic reaction to the fluoroscopic imaging contrast agent. Symptoms could include redness or inflammation at the injection site or inside the ankle joint, hives or itching.
- an allergic reaction to the local anesthetic (lidocaine). Symptoms could include redness or inflammation at the injection site or inside the ankle joint, hives or itching.
- injection site infection
- neurovascular, cartilage, or bone damage resulting from the injection itself

Finally, there is a low risk associated with radiation from the X-ray evaluation required for inclusion in the study. There is also a low risk from the radiation during fluoroscopy-guided injections

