### 6.4 Safety Endpoint:

The incidence, severity, and relationship to treatment of all Adverse Events (AE) will be collected from the treatment injection to the 6 month assessment.

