**6.6.4 Baseline Exclusion Criteria**

1. Subject has a decrease of  $\geq 2$  in the NRS pain on walking from Screening to Baseline in the index joint.
2. Subject has a contraindication to continue with the study treatment injection based on the visual appearance of the synovial fluid aspirate.

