##### **Treatment Procedure**

The Treating Physician will always perform the Study Injection to the index joint as standard of care dictates.

Intra-articular injection of the ankle joint should be conducted under fluoroscopic or ultrasound guidance. Guidelines for the injection procedural steps are provided below. Modifications to this technique should be recorded in the CRFs.

- Patient is supine.
- Prep the skin at injection site with 1% betadine solution or equivalent.
- Peri-articular injection site anesthesia of lidocaine or topical refrigerant anesthetic (e.g. ethyl chloride) may be utilized.
- The ankle is dorsiflexed to a neutral position. Injection site is located in the anteromedial portal of the ankle joint as described for ankle arthroscopy
- Fluoroscopic or ultrasound guidance may be utilized if required to insert 18-22 gauge needle. Traction can be applied if required to gain access.
- Insert needle until resistance against the articular surface and then withdraw the needle 1-2 mm.
- If using fluoroscopic guidance, a small amount of fluoroscopic contrast agent (0.5 to 1.0 ml) should be injected through the needle to verify intra-articular placement.
- If using ultrasound guidance, a small volume of air (up to 0.5 ml) may be injected to verify IA

positioning.

- If pooling of the contrast agent or air around the needle tip is observed, the needle should be repositioned.
- When contrast agent or air is successfully injected into the joint, intra-articular placement is confirmed.
- Following confirmation of intra-articular needle placement, the joint may be aspirated to remove synovial fluid.
  - Confirm the Baseline Exclusion for synovial aspirate.
- 2 ml of MONOVISC is injected into the joint.
- Intra-articular anesthetic should NOT be administered as part of the injection procedure.
- Following the injection, the patient should be advised to maintain a low level of physical activity for the next 48 hours. Cold therapy and/or acetaminophen/ paracetamol may be prescribed to address short term injection site pain.

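### A subject stopped at the synovial aspirate check has undergone part of the injection procedure but is outside the Safety Population, and the start of adverse event recording is ambiguous

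*Protocol*

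**What the plan says.** Three parts of the Protocol bear on this point.

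- **Order of steps.** Under Treatment Procedure in 7.4, skin preparation is followed by optional anaesthesia, needle insertion, and contrast or air to confirm placement. Then "the joint may be aspirated to remove synovial fluid", the aspirate exclusion is checked, and MONOVISC is injected. Section 6.6.4 excludes a subject with a contraindication to continuing, "based on the visual appearance of the synovial fluid aspirate".
- **Who is analysed for safety.** Section 9.2.3 states: "The Safety Population will be defined as all subjects who undergo Study Treatment". The synopsis ties all safety analyses to subjects treated with MONOVISC in the ankle.
- **When recording starts.** Section 9.2.2 states: "Adverse events occurring prior to the index treatment will not be recorded in this trial". Under 6.4, adverse events "will be collected from the treatment injection to the 6 month assessment". Section 8.1.1 states: "All AEs that occur during or after injection will be recorded", and adds: "All subjects will be questioned and evaluated for AEs or complications associated with the procedure".

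Section 4.2 lists rare harms of the early steps: "an allergic reaction to the fluoroscopic imaging contrast agent", a reaction to lidocaine, and structural damage caused by the needle. Section 9.2.2 plans summaries by relationship to product or procedure.

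**The concern.** Section 6.5 presents the study as an evaluation of residual risk from these injections. Some of the harms named in 4.2 arise from the anaesthetic, the contrast or the needle, and so can occur before any MONOVISC enters the joint. A subject who has had those steps and is then excluded contributes nothing to the safety analysis, even if an event occurs and the site writes it down.

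The second issue is the recording rule. If one site takes the index treatment to be delivery of MONOVISC and another takes it to be the whole procedure, they will record the same pre-MONOVISC event differently. The planned summaries by relationship to procedure would then rest on inconsistent data. An analysis plan cannot repair this, because it cannot recover events that a site did not record.

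**Working it through.** The Protocol states no figure on this point, so the main check is a comparison of its sections.

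**Step 1: what a stopped subject has received.** From 7.4, by the time of the aspirate check the needle has been inserted in every case. Anaesthesia is optional. Contrast (0.5 to 1.0 ml) is specified if fluoroscopy is used, and air may be injected if ultrasound is used. No MONOVISC has been given.

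**Step 2: whether that subject is in the safety analysis.** Section 9.2.3 requires Study Treatment, and the synopsis requires treatment with MONOVISC. The stopped subject has not had MONOVISC, so is left out of both the count of events and the number at risk. How the word injection is read in the recording rules does not change this.

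**Step 3: whether a pre-MONOVISC event is recorded.**

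| Section | If the term means MONOVISC delivery | If the term means the whole procedure |
|---|---|---|
| 9.2.2 (index treatment) | event barred | event not barred |
| 6.4 (treatment injection) | outside the window | inside the window |
| 8.1.1 (during or after injection) | not covered by that sentence, though the sentence on procedure complications points to recording | covered |

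Under the second column the three sections agree. Under the first, 9.2.2 and 6.4 pull against the procedure-complications sentence in 8.1.1 and against the planned summaries by procedure. The visit layout does not settle it. The pre-injection list in 7.4 has no adverse event assessment, the only one described for that day comes under the post-treatment heading, and the schedule in 7.1 marks one at Baseline without saying when in the visit.

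**Step 4: scale, under assumptions.** The documents give no stop rate. Take 25 treated subjects (9.1 aims to treat at least 25) and assume k further subjects stopped at the check. The share of needle-exposed subjects outside the Safety Population is k/(25 + k):

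- k = 1: 1/26 = 3.8%
- k = 2: 2/27 = 7.4%
- k = 3: 3/28 = 10.7%

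If each stopped subject has an assumed procedural event risk p, the chance that at least one event is left out is 1 − (1 − p)^k. With p from 1% to 10%:

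- k = 1: 1% to 10%
- k = 3: 1 − 0.99³ = 3.0% to 1 − 0.90³ = 27.1%

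Both k and p are assumptions and serve only to show scale.

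**The case against.** The strongest reply is that the layout of 7.4 already answers the recording question. Anaesthesia, needle, contrast and aspiration all sit under Treatment Procedure, apart from the list of activities before the injection. On that structure they belong to the index treatment, and 9.2.2 removes only events between consent and the procedure. Section 8.1.1 supports this: it asks every subject about procedure complications and wants events on the CRF whatever their relationship to the injection. Section 8.1.2 requires all serious events to be reported within 24 hours and gives no start point. A safety set of treated subjects is also a common convention.

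Much of this stands, and it rules out some stronger readings.

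- A reader might infer that pre-MONOVISC harms in subjects who go on to be treated are lost, so that one event in 25 (4%) would be reported as 0%. The documents do not establish that. Such subjects stay in the denominator, are evaluated before leaving the clinic, and are covered by 8.1.1 on its natural reading. Nor does that figure describe stopped subjects, who are not among the 25 treated.
- A reader might see a contradiction between optional aspiration and an exclusion based on the aspirate. There is none: the check is part of the optional step, and if nothing is aspirated the exclusion is not triggered.
- A reader might conclude that recording has to begin at informed consent. The gap shown here begins only with the procedure.

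The reply does not reach the stopped subject. Even if the event is recorded, or reported as serious, the definitions in the synopsis and 9.2.3 keep it out of the safety analysis.

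**Conclusion.** The point holds in two parts of different strength. The exclusion of stopped subjects from the safety analysis follows from the stated definitions on any reading. The recording problem is an ambiguity: 9.2.2 and 6.4 can be read to bar pre-MONOVISC procedural events, but do not have to be. The number affected is unknown and probably small, since aspiration is optional; the 3.8% to 10.7% range rests wholly on the assumed 1 to 3 stopped subjects. Any loss from recording would fall mainly on non-serious events. The effect is on the completeness of procedural safety data in a small study meant to describe residual risk.

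**What to change.** In 6.4, 8.1.1 and 9.2.2, state in the same words that adverse events are recorded from the first step of the injection procedure, and name that step.

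For the analysis set, in both the synopsis and 9.2.3, choose one of two options:

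- define the Safety Population as all subjects in whom the procedure was started; or
- keep the treated set and add a separate summary or listing of adverse events in subjects started but not given MONOVISC.

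The first option puts a few subjects who never received the product into the denominator of product-related rates (26 to 28 in place of 25 in the illustration). The second avoids that.

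The cost is a few sentences of wording and a few more adverse event entries, with a CRF flag for before or after MONOVISC if the two are to be reported apart. Sample size and the primary analysis do not change.
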